8.6. Study Exit Criteria and Procedures

All patients that sign an informed consent document for this study will have the study exit reason documented in the medical record and on the appropriate eCRF. Patients may exit the study for any of the following reasons:

- **Screen Failure:** Patients who are consented to participate in the study, but do not fulfill enrollment criteria.

- **Study Device Attempted but Not Implanted:** Enrolled patient for whom the implant procedure was prematurely aborted will be followed either for 30 days (for only safety evaluations) OR until resolution, stabilization, or is adequate explanation of any implant-related AEs and then exited from the study. Examples include:
 - Procedure attempted (i.e. skin incision to introduce the EVOQUE System) but patient did not receive a study device
- **Study Device Re-intervention/Explant:** Patient who has a surgical re-intervention for study device explant will be followed for 30 days after the re-intervention for safety evaluations only or until resolution of any AEs related to the re-intervention and then exited from the study. Note: a patient who has a percutaneous re-intervention where the study device remains in place will continue to be followed for the duration of the study.
- **Withdrawal**
 - **Patient Withdrawal:** A patient may voluntarily withdraw from the clinical study at any time, without penalty or loss of benefits to which they are otherwise entitled.
 - **Physician Withdrawal:** An Investigator also has the right to withdraw a patient if s/he feels it is in the best interest of the patient to do so.
- **Patient death**
- **Lost to Follow-up**
 - If a patient cannot be reached for a follow-up visit, the Investigator will document contact efforts and/or efforts to obtain hospital records in the appropriate eCRF. If a patient cannot be reached in any way, or misses a visit, the patient will be considered “unable to contact” for that time interval.
 - After 3 documented unsuccessful attempts to make contact, a certified letter will be sent to the patient’s residence. If there is no response after a certified letter is sent, the patient will be classified as “lost to follow-up”.
- **Completion Per Protocol**

Withdrawn patients will not have any study follow-up visits or procedures after the time of study exit. All data collected up until the time of withdrawal, including imaging studies such as echocardiography scans, will be analyzed.

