For patients lost to follow-up or withdrawn early, the Sponsor may request the site to search the Social Security Death Index and/or other death registries and, if applicable, request the site to obtain a death certificate.

Withdrawn or lost to follow-up patients will not be replaced.

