11.9. Investigational Device Explants

An Edwards' study device that is explanted at any time during the study should be returned to the Sponsor for evaluation.

Once the study device is explanted, the patient is followed for 30 days after the explant, unless there is an ongoing related adverse event and its outcome is not deemed resolved by the Investigator. Return kits for explanted devices will be provided upon request by the clinical monitor or study team.

12. Statistical Analysis

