#### DEFINITIONS 5.

#### 5.1 Analysis Dates and Days

Reference Start Date and Day 0

The reference start date is defined to be the date of the index procedure. The index procedure is defined as the time the first skin incision for the study device is established. If a patient has multiple procedure forms, information will be presented on the procedure with the first date when the site has indicated that the interventional skin incision for study device is performed. If no form has this indicated, then the procedure information corresponding to the date of the first procedure will be used.

The reference start date is considered to be day 0.

Last Participation Date

The Last Participation Date is defined as the last date the patient was seen (refer to the programming convention for complete details).

Last Participation Day

Last Participation Day = Last Participation Date – Reference Start Date

Note: Last Participation Day is used as censor day for Kaplan-Meier analysis.

	Revision Date: August 1, 2022		Rev		For Use Only by Affiliates of Edwards Lifesciences	Page 12 of 18
Edwards	Title	Statistical Analysis P	lan foi	 TRIS	CEND Study	r (2019-06)

• Study Day

Study Day = Date – Reference Start Date

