### 6. DATA AND ANALYSIS CONVENTIONS

#### 6.1 General Conventions

For continuous variables, results will be summarized with the number of observations, mean, standard deviation, median, minimum, maximum, and 90% confidence interval (CI) by normal approximation. For categorical variables, results will be summarized with patient count, percentage, and 90% CI by normal approximation, where appropriate.

Survival analysis techniques will be used to analyze time-to-event variables. Patients without events will be censored at their last participation date in the study. For patients who did not have an event but remain in the study, they will be censored at the database extract date. Time to first event curves will be constructed using Kaplan-Meier estimates. Descriptive statistics will be presented at each assessment, including change from baseline to subsequent time point for selected endpoints. For the determination of event rates, the number of patients in the patient population who have had the events or have been followed up to the upper bound of the follow-up visit window will be used as the denominator. Unless otherwise noted, patients with missing data will be excluded from the denominator.

When the sample size is small (e.g., <10 patients), analysis may be performed in the form of listings only.

Quality of life questionnaires will be scored according to algorithms provided by the vendor. The various summary scores produced by the algorithms will be analyzed as continuous variables.

Unless otherwise specified, confidence limits will be two sided, using alpha = 0.05.

Unless otherwise specified, the precise form of each algorithm will be the default of SAS, using the latest release installed at Edwards Lifesciences (Edwards) at the time of analysis.

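### All-cause mortality to 5 years can be biased, mainly in later years: vital status is not sought after a surgical explant, and the SAP has no rule for traced deaths or traced survivors

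*Protocol*

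**What the plan says.** **Exit after explant.** Protocol 8.6 says that a patient whose device is surgically removed "will be followed for 30 days after the re-intervention for safety evaluations only"; the stated alternative is to follow the patient until adverse events tied to that surgery have resolved. The patient then leaves the study. Protocol 11.9 is similar: "Once the study device is explanted, the patient is followed for 30 days after the explant, unless there is an ongoing related adverse event". By contrast, Protocol 8.6 keeps patients in full follow-up after a percutaneous re-intervention that leaves the device in place. Explant is listed as an exit reason separate from withdrawal and loss to follow-up. Protocol 6.3 says that all implanted patients are assessed out to 5 years and makes no exception for explants.

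**Tracing.** Protocol 8.6 provides: "For patients lost to follow-up or withdrawn early, the Sponsor may request the site to search the Social Security Death Index". Other death registries are also allowed. This is discretionary and does not name explant exits. The same section says that data collected up to withdrawal will be analysed. It does not say how a death found later is used.

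**Endpoint and population.** Protocol 5.4.1 and SAP 3.4.1 list all-cause mortality at 12 months and annually to 5 years. SAP 8.4 estimates it by Kaplan-Meier in the As-Treated population. SAP 4 defines that population by having the device in place on leaving the procedure room, so a later explant does not remove a patient from it.

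**Censoring.** SAP 6.1: "Patients without events will be censored at their last participation date in the study". SAP 5.1: "The Last Participation Date is defined as the last date the patient was seen", with details left to a programming convention that is not among the documents; a note adds that "Last Participation Day is used as censor day for Kaplan-Meier analysis". SAP 6.2 repeats the rule for withdrawn and lost patients. Censoring at the database extract date applies only to patients still in the study. Neither document plans a sensitivity analysis for informative censoring.

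**The concern.** Kaplan-Meier estimation needs censoring to be unrelated to prognosis. Leaving the study because the valve had to be removed surgically is a plausible breach. If these patients die at a higher rate than those who stay, censoring them about a month later lowers the mortality estimate, and the written exit rule makes this happen for every surgical explant.

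The tracing question is separate. If a registry death after the last visit is counted as an event, while a lost patient who is still alive stays censored when last seen, deaths enter without the matching survivor time. The estimate then rises even when loss has nothing to do with prognosis. The SAP text neither adopts nor excludes this.

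One study objective is to guide the design of later studies, so the late mortality figures are likely to be reused.

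**Working it through.** The plan has no figure to reproduce. It states no mortality, explant or loss rate, and SAP 2.3 says that the sample size of up to 200 has no statistical justification. Every rate below is an assumption.

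**1. Explants.** Assume 45% 5-year mortality without explant, a fraction f = 3-6% explanted, and mortality m = 60-80% over the 5 years after explant.
- If all explants came at the start and all later deaths were missed, the understatement would be f × (m − 45%).
- Low end: 0.03 × 15 = 0.45 points. High end: 0.06 × 35 = 2.1 points.
- Simulation of cohorts of 190 patients allows for deaths before explant and within the 30 days. Complete follow-up against the plan gives 45.4% against 45.0% (0.4 points) and 47.0% against 45.1% (1.9 points).
- With other assumptions (1-5% explanted, all in year 1; 1-year mortality 10% or 15%; hazard after explant 3 to 5 times baseline), the understatement is 0.1 to 0.9 points at 1 year and 0.3 to 2.4 points at 5 years.
- If the hazard does not change after explant, the bias is zero.

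**2. Registry deaths added, survivors left at date last seen.** This is conditional: the SAP does not say it will be done. Assume constant death hazard λ = −ln(0.55)/5 = 0.1196 per year, loss unrelated to prognosis with hazard μ = −ln(1 − L)/5, and complete capture of deaths. Lost patients who survive 5 years drop out of the risk set while every death stays in, so the estimated hazard is

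h(t) = λ / [1 − (1 − e^(−μt)) × S(5)/S(t)], with S(t) = e^(−λt).

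The true cumulative hazard is 5λ = 0.5978. The inflation factor h(t)/λ at 0, 2.5 and 5 years, averaged by Simpson's rule:
- L = 10%: 1, 1.040, 1.111; mean 1.045. Then 0.5978 × 1.045 = 0.625, and 1 − e^(−0.625) = 46.5%, or +1.5 points.
- L = 20%: 1, 1.085, 1.250; mean 1.098. Then 0.5978 × 1.098 = 0.657, and 1 − e^(−0.657) = 48.1%, or +3.1 points.

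Simulation gives about +1.4 to +3.0. If only half of the deaths are added (1-year mortality 10%, 10-20% lost, hazard after loss 1 or 2 times baseline), the 5-year effect is −0.1 to +1.6 points. With no tracing it is 0.0 if the hazard is unchanged after loss, and −1.3 to −2.7 if it doubles. All loss and tracing effects at 1 year are within 0.2 points.

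**3. Candidate remedies.** With true vital status for every lost or withdrawn patient, the tracing bias is 0.0 in every scenario run. A rule that censors everyone not found dead at the search date does less well, because it treats absence from a registry as being alive. Under the assumptions of step 2, with capture c, its bias is −(1 − c) × D, where D is the share of patients who die after loss but before year 5:

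D = μ/(μ + λ) × (1 − e^(−5(μ+λ))) − S(5) × L.

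- L = 10% (μ = 0.0211): 0.1498 × 0.505 − 0.055 = 2.07%.
- L = 20% (μ = 0.0446): 0.2718 × 0.560 − 0.110 = 4.22%.
- Capture 80% with 10% lost: −0.2 × 2.07 = −0.4 points. Capture 60% with 20% lost: −0.4 × 4.22 = −1.7 points (simulated: −1.6).

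Censoring when last seen, with no registry deaths added, is unbiased in that same setting.

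**4. Scale.** A simple binomial 95% half-width at 200 patients and 45% is 1.96 × √(0.45 × 0.55/200) = 6.9 points.

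**The case against.** The strongest reply is that the plan shows a gap in the text, not a demonstrated bias. Much of that stands.

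- **Registry deaths.** A reader might infer that the plan adds registry deaths without survivor time and so overstates mortality. No section says that a registry death after the last visit counts as an event. SAP 6.2 says only that lost and withdrawn patients are censored, and SAP 5.1 defers detail to a convention not supplied. The overstatement is a possibility under a silent SAP.
- **Explants.** Deaths within the 30 days, or while related adverse events continue, are captured. Percutaneous re-interventions with the device in place stay in follow-up, and non-elective re-intervention is its own endpoint. This narrows the explant problem to deaths after exit but does not remove it.
- **Attempted but not implanted.** A reader might think that their early exit also distorts this endpoint. It does not, because they are outside the As-Treated population. They matter only for Enrolled-population rates such as cardiovascular mortality in SAP 8.1.
- **One-year mortality.** A reader might extend the concern to all time points alike. The 1-year effects are under 1 point throughout the assumed ranges.
- **Stakes.** This is a single-arm feasibility study with a 30-day safety endpoint and no test or threshold for late mortality. The effects are smaller than the sampling error and the two mechanisms can offset. That limits the weight of the point, but the confidence interval does not reflect a systematic error, and any offset would be accidental.

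**Conclusion.** The concern holds as a risk of bias in late all-cause mortality. The explant part follows directly from the written exit and censoring rules and lowers the estimate if explanted patients die at a higher rate: about 0.4 to 1.9 points at 5 years with 45% 5-year mortality and 3-6% explanted with 60-80% mortality over the following 5 years.

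For lost and withdrawn patients, what can be shown is that tracing is optional and that its use in the analysis is unspecified. Only if deaths were added asymmetrically with complete capture would mortality be overstated, by about 1.4 to 3.0 points with 10-20% lost. None of these rates comes from the documents, so the net direction and size are unknown.

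**What to change.** **Protocol 8.6.** Extend vital-status ascertainment to explanted patients as well as lost and withdrawn patients in the As-Treated population, where consent allows. Do it for all of them on a fixed date before each annual data cut. Reconcile the explant exit with the 5-year assessment of all implanted patients in Protocol 6.3.

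**SAP 5.1, for all-cause mortality only.** Traced deaths count as events at the date of death. Patients confirmed alive are censored at the date of confirmation.

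**Where a registry is the only source.** Report two analyses: one censored at last participation without registry deaths, and one with registry deaths and censoring at the search date. Together they bracket the effect of incomplete capture when loss is unrelated to prognosis. If lost patients die at a higher rate, both can be too low, and the report should say so.

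**Cost.** A small number of look-ups or contacts each year and some consent wording, with no added study visits. Registry capture will remain imperfect.

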8.7. Imaging Assessments

Imaging assessments (TTE, TEE, and CT) shall be performed according to the current version of the acquisition manual/guide. For screening and baseline examinations, pre-existing TTE and TEE examinations obtained through standard of care treatment and within trial specified windows (Table 8, “Screening/baseline assessment windows”) may be used if they provide the required images/views to qualify anatomical inclusion/exclusion criteria and TR grade. For chest CT scan, a standard of care assessment of adequate quality capturing required anatomy for assessment can be used as the screening/baseline assessment, provided it is within 1 year prior to consent.

8.8. Screening/Baseline Examinations and Windows

If local IRB approval is obtained, a screening consent form may be implemented to enable the collection of standard assessments for this population (e.g., TEE and TTE). Data collected from screening assessments may be used to simultaneously assess the patient's anatomic eligibility for this Study or other Edwards Clinical Studies using a transcatheter tricuspid repair or replacement study device. If local IRBs do not allow the use of a screening consent form, all screening assessments will be described under the applicable standard study ICF.

Table 7 identifies the procedures and measurements that will be performed during baseline/screening. Data available in the patient's medical record may be utilized to fulfill requirements and do not need to be repeated if completed within 30 days prior to informed consent, unless otherwise noted in Table 8 (screening and Baseline Windows). If not previously completed, the following tests and procedures must be performed after informed consent and prior to submission to the Central Screening Committee. Additional repeat clinical information or laboratory measurements may be required prior to CSC case review or device implantation.

Table 7: Screening and Baseline Procedures

General Information	
 • Informed consent§ • Demographics • Inclusion/exclusion and other screening evaluation
Clinical Information	
 • Medical history (e.g., co-morbidities, EuroSCORE II, STS score (MV Repair and MVR), prior cardiovascular interventions / surgeries, paracentesis procedures) • Clinical Evaluation/Prior Recent Hospitalizations • Targeted physical exam, lower limb edema grading (+1-+4), and ankle circumference measurements • Concomitant Medications (including diuretic dose/s) • Modified Rankin Scale (mRS)† • Patient Edema Questionnaire • NYHA Classification • 12-lead ECG • 6MWT results • Health outcome questionnaires - KCCQ, SF-36v2 • Patient preference survey • Katz Index of Independence in Activities of Daily Living (Katz ADL) • Canadian Study of Health and Aging Survey Clinical Frailty Scale • Transthoracic echocardiogram (TTE) ‡, § • Transesophageal echocardiogram (TEE) ‡, § • Chest CT Scan § • Pulmonary function test, for patients with chronic lung disease (e.g., COPD) §

Laboratory Measurements ¶	
 • βHCG, for females of childbearing potential only§ • BNP or NT-proBNP • Coagulation panel (PT or PTT; INR for patients on vitamin-K antagonist) • Complete blood count (CBC; including platelets) • Comprehensive metabolic panel (CMP; including Albumin, Bilirubin, ALP, ALT, AST, creatinine, BUN) • GGT • Troponin or CK/CK-MB • Uric acid and eGFR
Sub-study Only§	Initiated at baseline, a minimum of 2 weeks prior to index procedure: 
 • eDiary collection • Activity monitoring

§ See Table 8 for associated assessment window

† mRS will be conducted at baseline for all patients with a history of stroke. For patients who experience a stroke during the study, mRS will be conducted closest to 90 days post-event. It is recognized that an assessment of stroke is incomplete without an appropriate measurement of the disability resulting from the stroke, hence, mRS closest to 90 days post event will be used to assess clinical disability. Every effort should be made to have a neurologist or neurology fellow perform the neurological assessments, or alternatively, a trained research team member certified in stroke assessment. mRS can be obtained by a certified research team member via phone interview with the patient or caregiver member if the patient is unable to visit the research office.^{53,54}

‡ All TTE and TEE imaging deemed incomplete or inadequate for assessment may require repeat imaging. If multiple echo (TTE or TEE) examinations are performed during the screening/baseline period, the most recent baseline echo (TTE or TEE) examination should be used to determine study eligibility.

¶ Repeated peri-procedurally per local institutional standard of care. Blood samples will be analyzed by local institution and any remaining blood sample will be discarded according to institutions regulations.

Table 8 provides the screening/baseline assessments windows if a patient has a pre-existing assessment. If a patient does not have an in-window assessment, the assessment should be collected after collection of ICF and prior to CSC case review.

Table 8: Screening/Baseline Assessment Windows

General Information	Window
Informed consent	Index procedure should be scheduled within 90 days of signing
TTE	A pre-existing TTE of adequate quality capturing required anatomy for assessment can be used as the screening/baseline assessment, provided it is within 60 days of submission to the study-specific image transfer system
TEE	A pre-existing TEE of adequate quality capturing required anatomy for assessment can be used as the screening/baseline assessment, provided it is within 180 days of submission to the study-specific image transfer system
Chest CT Scan	Standard of care assessment of adequate quality capturing required anatomy for assessment can be used as the screening/baseline assessment, provided it is within 1 year prior to consent
Pulmonary function test (for patients with chronic lung disease, e.g., COPD)	Standard of care assessment within 1 year prior to consent is acceptable

PROPRIETARY DATA: THIS DOCUMENT CONTAINS CONFIDENTIAL AND PROPRIETARY INFORMATION OF EDWARDS LIFESCIENCES, LLC. IT MUST NOT BE REPRODUCED OR DISCLOSED TO THIRD PARTIES WITHOUT PRIOR WRITTEN PERMISSION OF EDWARDS LIFESCIENCES, LLC.

Edwards Lifesciences, Edwards, the stylized E logo, and EVOQUE are trademarks of Edwards Lifesciences Corporation.

General Information	Window
βHCG, for females of childbearing potential	To be assessed via blood or urine test within 14 days prior to intervention in female patients of childbearing potential.
Sub-study: eDiary assessment*	Initiated at baseline; A minimum of 2 weeks prior to index procedure
Sub-study: Activity Monitoring Initiation*	Initiated at baseline; A minimum of 2 weeks prior to index procedure

* Applies to all patients participating in sub-study

8.9. Prior to Index Procedure

8.9.1. Pre-Procedure Therapy

Device Preparation

A description of device preparation and use is provided in the IFU. Investigators must be familiar with the information described in the IFU prior to use of the EVOQUE System. Edwards representative(s) that have been trained on the preparation of the EVOQUE System will be in attendance at all implant procedures.

Antibiotic Prophylaxis

All recipients will be prophylactically treated for endocarditis per institution's standard of care to minimize the possibility of infection.

Pre-Procedure Medical Therapy

Medical therapy in the 30 days prior to the procedure includes diuretic medications in stable doses, unless patient has documented history of intolerance. No new diuretics should be introduced and current diuretic doses should be stable (i.e. no decrease of more than ½ or increase of 2x) unless medically required (e.g., severe hypotension or signs and symptoms of hypervolemia).

8.10. Procedure

8.10.1. Contrast Media

Careful management of contrast media is required for these patients. Accurate measurement of the dye used during the implant procedure shall be captured in the appropriate case report form.

